3.6 Allocation

The treatment allocation sequence is generated using computer-generated random numbers. The assignment of treatment is based on the order of being eligible to participate in the study.

3.7 Blinding

Participants will be kept blind to the HA technology level. However, blinding participants to the services they receive is not feasible. Therefore, the study will employ a form of deception where participants will be informed that the trial has only one treatment arm and will be provided information solely on the services they receive. The research assistants responsible for collecting outcome data will remain blinded to the treatment assignment.

3.8 Participant timeline

Participants for this clinical trial will be recruited through print, radio, and online advertisements, as well as mass emails/letters to established registries/lists. The principal investigators of the trial will obtain consent from participants. Following enrollment, audiologists who are blinded to the treatment assignment will administer pre-intervention assessments. Participants will then start the one-week EMA-GHABP pre-intervention measure. Seven days later, participants will return to the laboratory where audiologists, now informed of the treatment assignment, will administer the interventions. A 6-week trial will then follow. At the end of the trial, participants will return to the laboratory where research assistants, who are blinded to the treatment assignment, will administer outcome measures. Participants will then start the one-week EMA-GHABP post-intervention measure. Seven days later, participants will return to the laboratory to complete the remaining outcome measures. Participants will be debriefed and compensated for their participation. Refer to Figure 1 for the participant timeline.

3.9 Adverse events

Adverse events will be monitored for each subject during their participation in the study, which average 8 weeks from the time the participants entered the study.

4 STATISTICAL ANALYSIS PLAN

Analyses will be conducted to determine the effect of service model, technology level, and their interaction on outcomes. For the primary outcomes, EMA-GHABP-Use and EMA-GHABP-Global, linear mixed models (LMM) will be used. LMM is selected because the primary outcomes will be collected using the EMA methodology and therefore consists of repeated observations within each participant. Linear regression models will be used for the secondary outcome dependent variables, including Retro-GHABP-Use, Retro-GHABP-Global, PHAP-Benefit, HHIE/A-Benefit, SADL, and CST-Benefit scores.

For all analyses, study site (Iowa and Tennessee) will be controlled for in the model. For both EMA-GHABP-Global and Retro-GHABP-Global, the pre-intervention GHABP scores will be controlled for in the model, with the repeated observations of pre-intervention EMA-GHABP-Global being averaged within each participant before being controlled for in the LMM. Pairwise comparisons (e.g., AUD vs. OTC+) will be conducted with an alpha level adjustment using the Tukey method. Two-tailed tests will be employed, with a significance level of .05. All statistical analyses will be performed using R statistical software.

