3.2 Eligibility criteria

3.2.1 Inclusion criteria:

- Adults between 55 and 85 years old
- Adult-onset, bilateral, mild-to-moderate sensorineural hearing loss
 - Pure-tone average across 500, 1000, 2000, and 4000 Hz between 25 and 55 dB HL
 - Thresholds from 500-4000 Hz no poorer than 65 dB HL, with up to 2 thresholds outside this criterion by < 10 dB still being eligible.
- No prior HA experience

3.2.2 Exclusion criteria:

- Non-native speaker of English

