3.3.1.1 AUD service model

In this service model, audiologists will fit prescription HAs according to the best practice guidelines. The fitting protocol will include the following measures: pure-tone audiometry to determine hearing threshold, the Client Oriented Scale of Improvement questionnaire (COSI)¹ to evaluate individual listening needs, measurement of loudness discomfort levels (LDL)^{2,3} to determine sound levels that are uncomfortably loud, and the QuickSIN⁴ to assess unaided speech recognition performance in noise. Audiologists will configure the HAs and select the appropriate slim tube length, ear dome size, and type for each participant based on assessment results, NAL-NL2 prescriptions,⁵ and their clinical experiences. Audiologists will then conduct probe-microphone real-ear measures to verify the gains of the HAs, and make further adjustments based on participant's feedback for comfort and sound quality. Additional hearing aid memories will be added and features will be adjusted based on the participants' listening needs. Audiologists will also provide orientation (e.g., insertion, removal, and care of devices, smartphone app installation and orientation) and counseling (e.g., establishing realistic expectations of amplification) services. Participants will have the flexibility to schedule follow-up appointments with audiologists as often as needed.

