3.3.1.2 OTC+ service model

In this service model, audiologists will provide services to fit preset-based OTC HAs. These services include conducting pure-tone audiometry to determine hearing thresholds and selecting the appropriate preset (from the four available presets, detailed below), slim tube length, ear dome size, and type. Selections will be based on the participant's audiogram, NAL-NL2 targets, and the audiologist's clinical experience. Audiologists can use the volume control and smartphone apps to make adjustments to the HAs as needed, but they will not use HA fitting software to program the devices as prescription HAs. Audiologists will also provide brief HA orientation and counseling. All services, except for pure-tone audiometry, will be completed in a 30-minute session. Participants will be allowed up to two follow-up visits of 15 minutes each for additional instruction or to address issues with the devices.

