3.3.1.3 OTC service model

In this service model, participants will self-fit preset-based OTC HAs. To self-select the OTC HA's preset, participants will use a Hearing Aid Selector kiosk app installed on a tablet computer to listen

to sounds recorded from each preset. The selection process will be conducted without assistance from audiologists. After selecting the preferred preset for each ear, participants will receive a package containing a pair of OTC HAs, which are simulated using prescription HAs (detailed below), and accessories including domes, slim tubes, and cleaning tools. The HAs will come with medium-length slim tubes and medium-sized dome tips of the style defaulted to the selected preset. The package will also include slim tubes of different lengths and various dome types in different sizes for replacement. During the trial period, participants will be permitted to return to the laboratory to reselect presets or request HA replacements if they encounter device-related issues they cannot resolve.

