3.4 Outcomes

3.4.1 Primary outcomes

3.4.1.1 In-situ Glasgow Hearing Aid Benefit Profile: HA use (EMA-GHABP-Use)

The GHABP⁸ is a questionnaire that measures HA users' listening experience in four situations: TV listening, small conversation in quiet, conversation in noise, and group conversation. The GHABP will be administered using smartphone-based Ecological Momentary Assessment (EMA) to collect in-situ self-reports. The GHABP items evaluate HA use averaged across the four listening situations form the EMA-GHABP-Use score. The score ranges from 1 (not use HA at all) to 5 (use HA all the time). The EMA-GHABP-Use will be measured between 6- and 7-weeks post-intervention for one week.

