3.4.1.2 In-situ Glasgow Hearing Aid Benefit Profile: Global score (EMA-GHABP-Global)

The EMA-GHABP-Global score is derived from the items of the in-situ GHABP that evaluate a patient's hearing disability, hearing handicap, HA benefit, and HA satisfaction across the four listening situations. This score ranges from 1 (poorer outcome) to 5 (better outcome). It will be measured for one week both pre-intervention and between 6 and 7 weeks post-intervention. During the pre-intervention assessment, only the items related to hearing disability and hearing handicap will be used.

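### The models for EMA-GHABP-Use, Retro-GHABP-Use and SADL adjust only for site, although two pre-treatment measures of severity are available; adding them is a nearly free gain in precision of unknown size.

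*Combined protocol and SAP*

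**What the plan says.** Section 4 fits service model, technology level and their interaction to every outcome and then states: "For all analyses, study site (Iowa and Tennessee) will be controlled for in the model". The pre-intervention GHABP score is added for EMA-GHABP-Global and Retro-GHABP-Global only. For the EMA version, the repeated baseline reports are first averaged within each participant. No audiometric measure appears in any model.

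Section 3.4.1.1 gives EMA-GHABP-Use a post-fitting assessment only: "The EMA-GHABP-Use will be measured between 6- and 7-weeks post-intervention for one week". Retro-GHABP-Use (3.4.2.1) and SADL (3.4.2.5) are also collected only after fitting. This follows from the entry rule "No prior HA experience": people who have never worn an aid have no use or satisfaction to report.

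Two measures of severity come before treatment:

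- **Pure-tone average.** Eligibility (3.2.1) requires "Pure-tone average across 500, 1000, 2000, and 4000 Hz between 25 and 55 dB HL".
- **GHABP disability and handicap items.** Of EMA-GHABP-Global, section 3.4.1.2 says "It will be measured for one week both pre-intervention and between 6 and 7 weeks post-intervention", with only these two item sets used at baseline. Section 3.4.2.2 provides the retrospective counterpart.

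Section 3.6 describes computer-generated random numbers and mentions no stratification by severity.

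**The concern.** The entry window for the pure-tone average spans 55 − 25 = 30 dB. How much loss and disability a person starts with could plausibly affect how much they wear an aid and how satisfied they are. If so, part of the spread in these three outcomes is predictable from data already in hand, and the planned models leave it in the residual.

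Two things are at stake. The service and technology contrasts would be less precise than they could be. And if severity happens to differ between groups, the analysis has no prespecified way to allow for it; an adjustment chosen after the data are seen would look selective. EMA-GHABP-Use matters most, because it is a primary outcome and the only one with an ITT analysis (4.1). Its candidate baseline covariate is already constructed, per participant, for the other primary outcome.

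**Working it through.** **Inputs from section 3.5:** difference 0.3 points; SD 0.53; 80 participants per service model; alpha 0.05/3 = 0.0167. Section 4 makes the tests two-sided.

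**1. Reproduce the stated power (no covariates).**

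- SE of a pairwise contrast = 0.53 × √(2/80) = 0.0838.
- Noncentrality = 0.3 / 0.0838 = 3.58.
- Normal approximation: critical value 2.394, power 88.2%.
- Exact noncentral t, 158 df: critical value 2.420, power 87.6%.

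The stated 88% is reproduced without any covariate.

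**2. Add the two covariates.** Let R² be the share of the variance behind the 0.53 SD that they explain jointly. The documents give no value, so the range is assumed. Residual SD = 0.53 × √(1 − R²); equivalent unadjusted n per service model = 80 / (1 − R²).

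| Assumed R² | Residual SD | SE | Equivalent n | Power (exact t) |
|---|---|---|---|---|
| 0% | 0.530 | 0.0838 | 80 | 87.6% |
| 5% | 0.517 | 0.0817 | 84 | 89.4% |
| 10% | 0.503 | 0.0795 | 89 | 91.1% |
| 20% | 0.474 | 0.0750 | 100 | 94.2% |

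If the covariates explain nothing, the cost is two degrees of freedom. Moving from 158 to 156 df lowers power by less than 0.01 percentage points.

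**3. Sensitivity to what the 0.53 contains.** Person-level covariates cannot reduce within-person variation. Suppose 30% of the variance is within-person (assumed). Then covariates explaining 10% of the between-person part explain 0.10 × 0.70 = 7% of the total. The SE is 0.0838 × √0.93 = 0.0808 and the equivalent n is 80/0.93 = 86, against 0.0795 and 89 above.

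**4. Chance imbalance.** With 80 against 80, the standardised difference in a baseline covariate lies within 1.96 × √(2/80) = 0.31 SD in 95% of randomisations. If the covariate correlates r with the outcome (assumed), an imbalance at that limit moves the unadjusted contrast by r × 0.53 × 0.31:

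- r = 0.2: 0.033 points, 11% of the 0.3-point target.
- r = 0.3: 0.049 points, 16% of the target.

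**5. Availability for ITT.** Section 4.1 defines ITT on everyone enrolled. In section 3.8 the EMA baseline week comes after enrolment. A participant who withdraws during that week may have no EMA baseline score, and a complete-case fit would drop that person from the ITT analysis.

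**The case against.** The case for leaving the plan alone is that nothing in it is invalid. Allocation is random, so the unadjusted contrast is unbiased, and its standard error and type I error already allow for chance imbalance. The power claim assumes no adjustment and is reproduced. The plan also follows a coherent rule: adjust where the outcome has a baseline on the same instrument. All of this stands.

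The benefit is also assumed. Neither the protocol nor the SAP links pure-tone average or baseline disability to aid use, and limiting entry to mild-to-moderate loss may weaken any link. At R² = 5% the gain is only 89.4 − 87.6 = 1.8 percentage points. Section 3.5 does not say whether the 0.53 refers to Use or Global, how much of it is within-person, or whether it is already adjusted. This stands too, and it limits the claim to a gain of unknown size.

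Three stronger readings are tempting, but the documents do not support them:

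- **That the audiogram serves only as an entry cut-off.** The AUD fitting protocol includes "pure-tone audiometry to determine hearing threshold" (3.3.1.1). For OTC+ (3.3.1.2), "Selections will be based on the participant's audiogram, NAL-NL2 targets, and the audiologist's clinical experience". Only for OTC is no fitting use described: "The selection process will be conducted without assistance from audiologists" (3.3.1.3). The accurate statement is that audiometry enters no analysis model.
- **That severity imbalance biases the result or undermines the 88%.** Randomisation rules out the first, and step 1 of the working rules out the second.
- **That the main contrasts rest on arms of 40.** Service contrasts compare 80 with 80, and the technology main effect compares 120 with 120.

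That a pure-tone average exists for every participant is an inference from the eligibility rule, since audiometry is named explicitly only in the AUD and OTC+ services. It is a safe inference, because eligibility cannot be decided without it.

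**Conclusion.** The point holds as a low-cost improvement and does not show an error in the plan. The models for EMA-GHABP-Use, Retro-GHABP-Use and SADL omit two pre-treatment severity measures that the trial already has. The consequence is a possible loss of precision and no prespecified correction for chance imbalance.

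At an assumed R² of 5% to 20%, power for a pairwise service contrast rises from 87.6% to between 89% and 94%. With R² of zero, nothing of consequence is lost. These figures treat the 0.53 SD as unadjusted, as applying to Use, and as the quantity from which R² is taken. The gain is smaller if part of that SD is within-person or if it is already adjusted. The figures do not carry over to the ITT analysis, where section 4.1 scores withdrawals as 0 and so changes the outcome's spread.

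**What to change.** In section 4, prespecify as fixed covariates in the models for EMA-GHABP-Use, Retro-GHABP-Use and SADL:

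- the four-frequency pure-tone average, continuous, with one stated ear rule (for example the better ear or the mean of both ears), since section 3.2.1 names no ear;
- the pre-intervention GHABP disability/handicap score: the participant's EMA average for EMA-GHABP-Use, and the retrospective score for Retro-GHABP-Use and SADL.

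Apply this in the PP analyses and, for EMA-GHABP-Use, in ITT as well. State that a missing covariate will be filled by simple baseline imputation, for example the overall mean, so that no enrolled participant is excluded for lacking one.

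The cost is a few sentences in the SAP and about two degrees of freedom per model. It needs no new data, visits or participant burden.

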3.4.2.3 Profile of Hearing Aid Performance (PHAP)

The PHAP⁹ is a questionnaire designed to measure the performance of HAs across various listening situations in seven domains. The scores of the five domains related to speech communication will be averaged to derive the PHAP score. The score ranges from 1 (good performance) to 99 (poor performance). Participants will complete this questionnaire pre-intervention and at 7 weeks post-intervention. The difference between pre- and post-intervention scores (benefit score; referred to as

PHAP-Benefit) will be used in the analysis. PHAP-Benefit ranges from -99 (intervention is detrimental) to 99 (intervention is beneficial).

3.4.2.4 Hearing Handicap Inventory for the Elderly (HHIE) or Hearing Handicap Inventory for Adults (HHIA)

The HHIE¹⁰ and HHIA¹¹ are questionnaires designed to measure participant's perceived hearing handicap. For participants aged 65 and over and younger than 65 years old, the HHIE and HHIA will be used, respectively. The score ranges from 0 (no handicap) to 100 (more handicap). Participants will complete this questionnaire pre-intervention and at 7 weeks post-intervention. The difference between pre- and post-intervention scores (benefit score; referred to as HHIE/A-Benefit) will be used in the analysis. HHIE/A-Benefit ranges from -100 (intervention is detrimental) to 100 (intervention is beneficial).

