3.4.2.6 Connected Speech Test (CST)

The CST¹³ is a speech recognition test designed to simulate daily speech communication. The CST will be administered in a sound-treated booth. Speech and noise will be presented at 0 and 180 degrees azimuth at a +3 dB signal-to-noise ratio (speech = 65 dBA). The score ranges from 0 (understand no speech) to 100 (understand all speech). Participants will complete this test pre-intervention and at 6 weeks post-intervention. The difference between pre- and post-intervention scores (benefit score; referred to as CST-Benefit) will be used in the analysis. CST-Benefit ranges from -100 (intervention is detrimental) to 100 (intervention is beneficial).

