3.5 Sample size

The trial is designed to detect a 0.3-point difference in the primary outcome GHABP. This difference is considered a minimal important change (MIC), as participants would prefer one HA intervention over another if they had the opportunity to try both.¹⁴ Power calculations are conducted for post-hoc comparisons of the main effects, specifically the pairwise comparisons between AUD, OTC+, and OTC. Based on the MIC and an estimated standard deviation from prior research (0.53 points), a two-sample t-test would achieve 88% power to detect a difference of 0.3 points, using a conservative Bonferroni adjustment to the alpha level of 0.0167 (0.05/3), assuming 40 participants in each of the six arms, totaling 80 participants in each service model for the pairwise comparisons. Therefore, a total of 240 participants will complete the trial, with 120 participants in each study site.

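### PHAP-Benefit, HHIE/A-Benefit and CST-Benefit are analysed as raw change scores without their own pre-intervention score as a covariate, which gives up precision the collected data allow

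*Combined protocol and SAP*

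**What the plan says.** Three secondary outcomes are defined as differences between a pre-intervention and a post-intervention score.

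- **PHAP** (Section 3.4.2.3), before the intervention and at week 7: the difference, "PHAP-Benefit) will be used in the analysis".
- **HHIE/A** (Section 3.4.2.4), same two time points: "The difference between pre- and post-intervention scores (benefit score; referred to as HHIE/A-Benefit) will be used in the analysis".
- **CST** (Section 3.4.2.6), before the intervention and at week 6: "The difference between pre- and post-intervention scores (benefit score; referred to as CST-Benefit) will be used in the analysis".

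Section 4 sets the models. The terms of interest are given by "Analyses will be conducted to determine the effect of service model, technology level, and their interaction on outcomes". For the secondary outcomes, "Linear regression models will be used for the secondary outcome dependent variables, including Retro-GHABP-Use, Retro-GHABP-Global, PHAP-Benefit, HHIE/A-Benefit, SADL, and CST-Benefit scores". Two sentences deal with covariates. One covers every model: "For all analyses, study site (Iowa and Tennessee) will be controlled for in the model". The other covers two outcomes only: "For both EMA-GHABP-Global and Retro-GHABP-Global, the pre-intervention GHABP scores will be controlled for in the model".

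No other part of the document adds the pre-intervention PHAP, HHIE/A or CST score to a model, or says why it is left out.

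**The concern.** Subtracting a baseline is not the same as adjusting for it. Subtraction assumes that each extra point before the intervention carries over as exactly one extra point afterwards. Where that slope is not 1, the change score keeps baseline noise that a covariate would remove. Two things follow: wider confidence intervals than the same data allow, and service-model or technology contrasts that move with any chance baseline difference between groups.

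The plan gives some reason to doubt a slope of exactly 1. The scales are bounded. HHIE/A benefit cannot exceed a participant's own pre-intervention score, and CST benefit cannot exceed 100 minus that score, so room to improve depends on baseline. Section 3.6 describes no stratification on these scores, so any chance imbalance is left to the analysis to handle.

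Precision is at stake, not validity. Under randomisation the change-score contrasts are unbiased.

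**Working it through.** **The plan's own figure.** Section 3.5 states 88% power for the primary GHABP outcome (difference 0.3, SD 0.53, two-sided alpha 0.0167, "totaling 80 participants in each service model for the pairwise comparisons"). The standardised difference is 0.3 / (0.53 × √(2/80)) = 3.58. Power is 0.882 by the normal approximation and 0.876 by the noncentral t with 158 df, so the figure reproduces. It does not depend on the present point. The plan gives no power or precision figure for PHAP, HHIE/A or CST.

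**Inputs.** Group sizes (80 vs 80; six arms of 40; 240 completers) come from Section 3.5, and the model terms from Section 4. The pre-post correlation r and the ratio k = SD(post)/SD(pre) are not in the documents. They are assumed and shown over a range.

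**Formulas**, in units of SD(pre)²:

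- Change score: 1 + k² − 2rk.
- Baseline-adjusted: k²(1 − r²). The treatment contrast is the same, apart from sign, whether the dependent variable is the Benefit score or the post score.
- Difference between the two: (1 − rk)². Here rk is the slope of post on pre. The difference is never negative, and it is zero only at slope 1.
- Ratio, adjusted over change: k²(1 − r²)/(1 + k² − 2rk), which is (1 + r)/2 when k = 1.

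**Results with equal SDs (k = 1):**

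| r | variance ratio | SE smaller by | adjusted n per group matching 80 on change scores |
|---|---|---|---|
| 0.3 | 0.65 | 19% | 52 |
| 0.5 | 0.75 | 13% | 60 |
| 0.7 | 0.85 | 8% | 68 |
| 0.8 | 0.90 | 5% | 72 |
| 0.9 | 0.95 | about 3% | 76 |

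The last column is 80 × the ratio.

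**Unequal SDs**, with k from 0.7 to 1.25 and r from 0.3 to 0.8:

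- Lowest ratio (r = 0.3, k = 0.7): 0.49 × 0.91 / (1 + 0.49 − 0.42) = 0.4459/1.07 = 0.42.
- Highest ratio (r = 0.8, k = 1.25): 1.5625 × 0.36 / (1 + 1.5625 − 2) = 0.5625/0.5625 = 1.00. The slope there is 0.8 × 1.25 = 1.

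**Simulation of the planned model** (six arms of 40, site, AUD vs OTC main-effect contrast, 3,000 runs per setting). The ratios of estimated variance were 0.653, 0.753, 0.854, 0.904 and 0.954 for the five rows above. They were 0.419 at r = 0.3, k = 0.7, and 1.005 at r = 0.8, k = 1.25. Mean error was about zero with and without the covariate.

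**Chance imbalance at 80 vs 80.** The baseline mean difference has standard error √(2/80) = 0.158 SD(pre). An imbalance of 1.96 standard errors is 0.31 SD. It shifts the change-score contrast by (1 − slope) × 0.31: 0.155 SD at slope 0.5, 0.062 SD at slope 0.8, and 0 at slope 1.

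**The case against.** **The difference from GHABP-Global has a reason.** Sections 3.4.1.2 and 3.4.2.2 say that the pre-intervention GHABP uses only the disability and handicap items, so no like-for-like change score exists and a covariate is the natural way to use the baseline. PHAP, HHIE/A and CST can be subtracted. This stands, and the contrast is therefore no proof of an oversight. It explains why GHABP-Global is not a change score. It does not explain why the slope is fixed at 1 for the other three.

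**The baseline is not ignored.** The Benefit score already uses it. That is right: the question is a fixed against an estimated slope.

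**The size is assumed.** This also stands. The ratio of 0.42 is one corner of an assumed grid. With equal SDs and r between 0.7 and 0.9, the standard error falls by only about 3% to 8%. For a given pair of groups, an imbalance of 1.96 standard errors is exceeded only about 5% of the time. Very close to slope 1, estimating the covariate costs slightly more than it gains, as the simulated 1.005 shows.

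**A prespecified change score is legitimate, and timing may matter.** The first part is true. On timing, the study began in 2018 (Section 3.3.2) and the reference list includes a 2024 publication. The documents do not say whether outcome data had been examined when this text was written. That bears on how the change is labelled, not on whether the adjusted analysis is the better one.

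**Conclusion.** The concern holds. Three of the six secondary outcomes are analysed with the baseline slope fixed at 1, although the pre-intervention scores are in hand and the plan already uses baseline covariates elsewhere. Under the assumption of equal pre and post SDs, adjustment would cut the variance of the treatment contrasts by 5% to 35% for r between 0.9 and 0.3. With unequal SDs the saving ranges more widely, down to none at slope 1. Neither r nor the SDs can be taken from the documents.

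This is a worthwhile efficiency gain rather than an error of validity. No result becomes invalid, and the primary analyses, the 88% power and the sample size of 240 do not change. One supporting point depends on dropout: Section 4.1 limits the intention-to-treat analysis to EMA-GHABP-Use, so these three outcomes are analysed in completers. If dropout related to baseline differently by arm, adjustment would remove the part of the resulting imbalance that a linear model captures.

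**What to change.** In Section 4, extend the baseline-adjustment sentence so that the PHAP-Benefit, HHIE/A-Benefit and CST-Benefit models each include the pre-intervention score of the same measure as a covariate, alongside site, service model, technology level and their interaction. The Benefit scores can remain the dependent variables, so effects keep their present units and direction.

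The cost is one sentence and one degree of freedom per model: 240 − 6 arms − 1 for site = 233 residual df, falling to 232. No new data are needed. No participant is lost, because a Benefit score cannot be computed without the pre-intervention score. If outcome data have already been examined, date the change and report the site-only models beside the adjusted ones.

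### Two primary outcomes are each tested at .05 with no rule linking them; if either counts, the chance of a false service-model claim is about 7–10%, not 5%

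*Combined protocol and SAP*

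**What the plan says.** Section 3.4.1 lists two primary outcomes. Both come from the same smartphone questionnaire, answered by the same participants. For Use (3.4.1.1), "The EMA-GHABP-Use will be measured between 6- and 7-weeks post-intervention for one week". For Global (3.4.1.2), "The EMA-GHABP-Global score is derived from the items of the in-situ GHABP that evaluate" disability, handicap, benefit and satisfaction; its post-intervention assessment falls in the same week.

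Section 4 treats the two alike: "For the primary outcomes, EMA-GHABP-Use and EMA-GHABP-Global, linear mixed models (LMM) will be used". On error control it says "Two-tailed tests will be employed, with a significance level of .05" and "Pairwise comparisons (e.g., AUD vs. OTC+) will be conducted with an alpha level adjustment using the Tukey method".

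Section 3.5 speaks of a single score: "The trial is designed to detect a 0.3-point difference in the primary outcome GHABP". It allows for the three service-model pairs, "using a conservative Bonferroni adjustment to the alpha level of 0.0167 (0.05/3"), and for nothing further. It does not say whether the SD of 0.53 belongs to Use or to Global.

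Section 4.1 also refers to Use as the primary outcome in the singular, but only to limit the intention-to-treat analysis to that score. It does not rank the two.

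**The concern.** Tukey's method protects the comparisons among groups within one model. Each primary outcome has its own mixed model, so each carries its own 5% chance of a false service-model claim. There are six primary service-model comparisons (three pairs on two outcomes), and the plan adjusts for three.

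The plan also leaves open what would count as a positive result: a difference on either score, on both, or on one named score first. With no stated rule, that choice can be made after the results are seen. Section 3.5 shows that the sponsor already wants false claims across service-model comparisons controlled, so leaving out the second outcome does not fit the plan's own standard.

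**Working it through.** **Inputs from the documents.** Difference 0.3, SD 0.53, 80 participants per service model (40 in each of six arms), stated power 88% at two-sided 0.05/3 (section 3.5). Two primary outcomes, two-tailed .05, Tukey for pairwise comparisons (section 4).

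**Assumptions.** The correlation between the two scores is not given, so 0 to 0.9 is shown. Each participant contributes one normally distributed summary score per outcome, in place of the mixed model. SD 0.53 is used for both scores.

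**1. The plan's own power figure.**
- Noncentrality = 0.3 / (0.53 × √(2/80)) = 0.3 / 0.0838 = 3.58.
- A two-sample t-test with 158 df at two-sided 0.05/3 gives 87.6%, which reproduces the stated 88%.

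**2. Error under the plan, no true differences.** Tukey at .05 with three groups and 237 df uses q = 3.335, that is |t| > 3.335/√2 = 2.36. Each outcome alone is held at 5%.
- Correlation 0: 1 − 0.95² = 9.75%.
- Correlation above 0: simulation of three group means on two correlated outcomes with pooled variances, 1,000,000 trials per value.

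| Chance of at least one false service-model claim | r = 0 | r = 0.5 | r = 0.7 | r = 0.9 |
|---|---|---|---|---|
| Plan as written, either outcome counts | 9.75% | 9.2% | 8.5% | 7.2% |
| Tukey at .025 for each outcome | 4.9% | 4.7% | 4.4% | 3.7% |
| Holm over all six unadjusted pairwise p-values | 4.5% | 4.3% | 4.0% | 3.4% |

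For Tukey at .025 and correlation 0, the arithmetic check is 1 − 0.975² = 4.9%. The plan's rate returns to 5% only at a correlation of 1.

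**3. Error when some differences are real.** Suppose AUD differs strongly from the other two models on one outcome only. The true nulls left are OTC+ versus OTC on that outcome and all three pairs on the other. At correlation 0:
- Plan as written: a single pair exceeds |t| = 2.36 with probability 1.92%, so 1 − (1 − 0.0192)(1 − 0.05) = 6.8%.
- Tukey at .025 each (q = 3.711, |t| > 2.62; single pair 0.93%): 1 − (1 − 0.0093)(1 − 0.025) = 3.4%.
- Holm over six p-values: 4.5% (simulated).
- Holm across the two outcomes with Tukey inside each: 5.9% (simulated). This procedure does not hold 5%.

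At correlation 0.5 the four figures are 6.6%, 3.3%, 4.4% and 5.8%.

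**4. Power for one pair (0.3 points, 80 versus 80).**

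| Test | SD | Power |
|---|---|---|
| Bonferroni 0.05/3 | 0.53 | 87.6% |
| Tukey .05 | 0.53 | 88.8% |
| Tukey .025 | 0.53 | 82.9% |
| First Holm step, 0.05/6 | 0.53 | 81.7% |
| Tukey .05 | 0.60 (assumed) | 79% |
| Tukey .025 | 0.60 (assumed) | 70% |

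With 90 per service model, Tukey .025 at SD 0.53 gives 87.9%.

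**The case against.** The strongest reply is that the documents never say a result on either outcome suffices. Use and Global measure different things, and the objective in section 2.2 concerns patient outcomes generally. If each score is reported as a question in its own right, Tukey at .05 holds error at 5% per question, and whether two distinct primaries must share one error budget is partly a matter of judgement. If both had to be significant, the false-claim rate with no true differences would be only 0.3% at correlation 0 and 2.8% at 0.9. This stands as a limit on the claim: the 7–10% figure depends on the either-counts reading. It does not remove the gap, because the plan adopts none of these positions.

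Second, two scores from one questionnaire in one week are unlikely to be uncorrelated, so the top of the range is less plausible. That is fair, but from 0.5 to 0.9 the rate is still 9.2% to 7.2%.

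Third, the calculation is not the planned mixed model. Adjustment for the pre-intervention score, planned for Global only, could change its residual SD and the correlation. This affects the decimals and the power figures; inflation remains at any correlation below 1.

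Fourth, a prespecified testing order or a both-required rule would also close the gap, and the power loss belongs to the remedy chosen. That is true. These are valid alternatives and do not make an alpha split unsound.

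**Conclusion.** The concern holds. The plan has two primary outcomes, each tested at two-sided .05, and no decision rule across them. If significance on either outcome is taken as a finding, the chance of at least one false service-model claim is 9.75% at correlation 0, falling to 7.2% at 0.9, against a nominal 5%. The figures rest on the either-counts reading, an assumed range of correlation, and one normal summary score per participant. They cover the service-model comparisons only; technology level and the interaction, also tested on both outcomes, would add to them. The stated 88% power is correct for a single outcome and is not in dispute. This is an inexpensive improvement that should be made; it does not invalidate the design.

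**What to change.** In section 4, state that the service-model comparisons on EMA-GHABP-Use and EMA-GHABP-Global form one family, and test them with Tukey at .025 for each outcome. Holm over all six unadjusted pairwise p-values is an acceptable alternative. Do not apply Holm across the outcomes with Tukey inside each, for the reason in step 3 of the working. Label the technology-level and interaction tests as outside this family. If the team prefers a testing order or a both-required rule, it should be written down in full, including how it applies to individual pairs, with its own power.

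In section 3.5, say which GHABP score the SD of 0.53 and the power refer to, and restate power as about 83% (Tukey .025), or about 82% as a floor for Holm.

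The cost is wording in two sections and about 5 points of stated power, with no added participants. Keeping about 88% under Tukey .025 would take about 90 per service model, 3 × 90 = 270 in all instead of 240. If either score has a larger SD than 0.53, its power is lower, as the 0.60 rows in the working show.
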